Interested participants will fill out a brief questionnaire to confirm eligibility either online or over the phone with research staff. Participants will be asked a series of questions regarding their tobacco product usage, health status, willingness to travel to Columbus for study visits, and brief demographic and contact information. Research staff will review the screener questionnaire for eligibility and inform participants if they are eligible for this study or not. Research staff will provide a study overview, discuss study procedures, and ascertain participant interest. Should the participant wish to proceed, research staff will schedule the first visit and communicate IRB-approved guidance, such as the CTR address and the need for subjects to abstain from tobacco products for 12 hours prior to the study visit. Participants will be advised that each research visit must be scheduled 2 or more days apart and that they must bring their own brand of cigarettes to the study visits in case they are randomized to smoke cigarettes at a particular visit.

Clinic Visits

Aim 1: Participants will be invited to the CTR to complete study procedures. At visit 1, informed consent will be collected. During visits 1-3, participants will complete an exhaled CO test, take a pregnancy test if applicable, a line will be placed for IV blood draw by the staff research nurse for IV blood draws throughout the course of the study visit, and be asked to either smoke their usual brand or insert a 3mg or 6mg NP and then sit in the room for 60 minutes. At each visit, participants will be randomly assigned to use 3mg Wintergreen pouches, 6mg Wintergreen pouches or their own brand of cigarettes. Participants will be asked a series of 3 questionnaires before, during, and after each product is used. Blood draws will be collected from the line at 0 5, 15, 30, 60, and 90-minutes. 3mLs, or a little less than 1 teaspoon, of blood will be drawn at each timepoint.

Measures of craving and withdrawal relief will be assessed at each blood draw (see attached surveys). If a collection interval is not met there will be no draw retroactively. Participants will be assessed for AE throughout procedures and prior to leaving the visit.

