Aim 2: Participants will be invited to the CTR to complete study procedures. At visit 1, informed consent will be collected. During visits 1-3, participants will complete an eCO test, take a pregnancy test if applicable, a line will be placed for IV blood draw by the staff research nurse for IV blood draws throughout the course of the study visit, and be asked to either try a 3mg NP or a synthetic NP and then sit in the room for 60 minutes. Participants will be asked a series of 3 questionnaires before, during, and after each product is used. Blood draws will be collected from the line at 0 5, 15, 30, 60, and 90-minutes. 3mLs, or a little less than 1 teaspoon, of blood will be drawn at each timepoint.

Measures of craving and withdrawal relief will be assessed at each blood draw (see attached surveys). If a collection interval is not met there will be no draw retroactively. Participants will be assessed for AE throughout procedures and prior to leaving the visit.

Inclusion/Exclusion Criteria

Aim 1: Adults aged 21 and older who reside in an Ohio Appalachian county and smoke at least 5 cigarettes per day will be considered for this project. Smokers who use other tobacco products (e.g., SLT, electronic cigarettes) > 10 days a month will be ineligible because our goal is to characterize the abuse liability of NPs among those who exclusively or primarily smoke cigarettes.

Inclusion	Exclusion
Age 21 years or older	Use tobacco products other than cigarettes >10 days per month.
Reside in an Ohio Appalachian county or surrounding rural area	Use NP in the past 3 months
Willing to complete study procedures, including abstaining from all tobacco,	Unstable or significant psychiatric conditions (past and stable conditions will be allowed)

nicotine, and marijuana for 12 hours before clinic visits	
Ability to read and speak English	Pregnant, planning to become pregnant, or breastfeeding
Smoke at least 5 cigarettes per day for the past 30 days	History of cardiac event or distress within the past 3 months
	Currently attempting to quit all tobacco use
	Self-reported diagnosis of lung disease including asthma (if uncontrolled or worse than usual), cystic fibrosis, or chronic obstructive pulmonary disease

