Participants will need to abstain from tobacco and nicotine products for ≥ 12 hours prior to their study visit. To check for abstinence from tobacco, participants will perform exhaled carbon monoxide testing ($eCO < 10\text{ppm}$) and confirm via self-report that they have not used any other nicotine products over the last 12 hours.

Pregnancy Test

All subjects capable of becoming pregnant will need to take and produce a negative pregnancy test in order to proceed further.

Pre-intervention questionnaire to be administered

This questionnaire will assess sociodemographics, tobacco use history, NP use history, and nicotine dependence. These questionnaires will be administered during Visit 1.

IV line insertion

Because blood draws will occur at set intervals, an IV line will be inserted by a trained staff nurse.

Blood draw to obtain baseline plasma nicotine levels

Next, participants will be reminded that in addition to the exhaled CO test, their abstinence will be confirmed at the time of visit via blood plasma nicotine analysis. 3 mL venous blood sample will be collected for later analysis to confirm abstinence. This blood draw will also be used to establish baseline plasma nicotine levels to estimate total nicotine delivery.

Administer intervention

Aim 1: The participant will receive a 3mg NP, 6mg NP, or be asked to smoke one cigarette of their usual brand depending on the randomization assignment. If smoking a cigarette, participants will be asked to smoke one cigarette following a standardized puffing protocol: they will take one puff every 30 seconds for 5 minutes. If using an NP, participants will be asked to place the pouch between their upper lip and gum and leave it in place for 30 minutes.

Aim 2: The participant will receive a 3mg tobacco-derived NP or a 3mg synthetic NP on randomization assignment. Participants will be asked to place the pouch between their upper lip and gum and leave it in place for 30 minutes.

Peri-intervention questionnaire to be administered

The QSU and MNWS surveys will be administered while at each blood draw interval of 0, 5, 15, 30, 60, and 90 minutes.

Post-intervention questionnaire to be administered

Measures of product appeal and behavioral intentions will be assessed after the participant has the cigarette or NP (Aim 1) or the tobacco-derived vs. synthetic NP (Aim 2).

Schedule return visit and provide gift card for participation

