Schedule return visit per subject and interviewer availability that is >2 days after the current visit. Provide \$100 via Clincard for their participation out of the up to \$350 possible. If it is their last visit has been completed within 1 month from consent, they will receive \$150 during their last visit.

Post-Enrollment Survey

6 months after enrolling, participants from Aims 1 and 2 will be recontacted via phone, text, and email for the opportunity to participate in a short online REDCap survey. Participants will complete a short consent addendum and respond to survey questions regarding their current tobacco product use and opinions surrounding nicotine pouches. For their time, they will receive a \$10 Amazon gift code.

Procedure Manual

Study procedures, including conducting pregnancy tests, blood draws, blood processing and analysis, gift card administration, and other procedures will be thoroughly explained in the study procedure manual.

4. Study Administration

Randomization, Blinding, and Unblinding

Participants will be randomized within the secure database, REDCap. The randomization piece involves at which of the 3 visits they are to use each product (Aim 1: 3mg NP, 6mg NP, or their own usual brand cigarette and Aim 2: the tobacco-derived 3mg tobacco-derived NP or the 3mg synthetic pouches). Participants will be blinded during study visits and at the end of their third visit will be informed which product they had at each visit.

Study Timelines, Number of Sites, and Enrollment

Participant Timeline

There will be a total of 3 study visits and 1 online survey opportunity 6 months after the completion of the final study visit. The study timeline for each participant will vary. Clinic visits can be completed in as little as a week and a half or as long as 2 months, but will ideally be completed within 3 week's timeframe for retention and administrative purposes. The study visits will take approximately 3 hours each. The online survey will take approximately 10 minutes to complete and will be offered 6 months after completing the final visit.

Duration of Study

We anticipate the clinical trial to take six months to complete. After that, we anticipate that it will take 1-1.5 years to clean and analyze data and disseminate results.

Total Number of Study Sites

All recruitment and enrollment activities will be completed within the CTR.

Total Number of Subjects Projected

55 subjects will be enrolled and each subject must meet I/E criteria.

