While this trial is not without risk, every effort will be taken to reduce risk and undue burden on participants.

Efforts to reduce risk are as follows:

1. Risk of using NP: The risk of side effects and adverse events are very low. Whether using tobacco-derived or synthetic nicotine, these products are sold online, and at specialty stores and convenience stores nationwide, without a prescription. Nevertheless, all participants will be screened for general medical precautions (pregnancy, cardiovascular disease) and monitored for adverse events during the study period. Study personnel will assess for adverse events via self-report at all follow-up visits. Subjects will also be provided a study phone line to report an adverse event between follow-up visits. Any serious adverse events will be reported to the PI and then to the OSU IRB and potentially to the NIH. We will withdraw participants who have a serious adverse event, or become pregnant or begin to breastfeed. The most likely adverse (potential for nicotine overdose) event is anticipated to be rare (<5% in our previous studies) and mild (nausea, headache, disrupted sleep) event will be handled quickly (i.e., advice to participant to reduce or stop NP use). Our on-site research nurse will also be available to escalate issues as needed and to handle any questions regarding reported adverse events. Lab studies of toxin exposure suggest that NPs incur no greater risk to health than do conventional cigarettes. Moreover, these are all over the counter products and are not significantly different from what the participant typically uses.

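### Beyond the 12 hours before each visit, nicotine pouch use between visits is neither restricted nor recorded, so product-dependent home use could affect later appeal and intention ratings unseen

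*Combined protocol and SAP*

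**What the plan says.** Section 2, Inclusion/Exclusion Criteria, lists "Use NP in the past 3 months" as an exclusion in both aims.

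Section 3 describes the pre-intervention questionnaire: "This questionnaire will assess sociodemographics, tobacco use history, NP use history, and nicotine dependence". It continues: "These questionnaires will be administered during Visit 1".

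At every visit, section 3 (baseline exhaled CO test) applies an abstinence rule: "Participants will need to abstain from tobacco and nicotine products for ≥ 12 hours prior to their study visit". It is checked by exhaled CO below 10 ppm, by asking participants to "confirm via self-report that they have not used any other nicotine products over the last 12 hours", and by a baseline plasma nicotine sample.

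Section 2, Clinic Visits, describes visits 1 to 3 in both aims and says: "Participants will be asked a series of 3 questionnaires before, during, and after each product is used". It does not give the content of the questionnaire that comes before product use.

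Section 4, Participant Timeline, says the visits can take "as little as a week and a half or as long as 2 months", with about 3 weeks as the ideal. The next documented question about tobacco use is the 6-month survey, after all product ratings are complete.

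Statistical Considerations tests the main effect of product with a random subject effect. Age, sex and other tobacco use enter only if unbalanced. No term for period, sequence or between-visit use is named.

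Section 5, Risk-Benefit Assessment, describes the handling of mild adverse events as "advice to participant to reduce or stop NP use", although the trial gives single pouches in the clinic.

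**The concern.** Recent pouch experience disqualifies a person at entry, but the trial then supplies that experience and does not follow what happens next. A participant who buys pouches after visit 1, or starts a quit attempt, would reach visits 2 and 3 with nothing in the data to show it, provided the 12-hour rule was kept.

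The outcomes at risk are product appeal and intentions to use or switch, which are rated at each visit. They carry part of hypothesis 1b (6 mg more appealing than 3 mg, with stronger intentions) and the second Aim 2 hypothesis (tobacco-derived more appealing than synthetic). If home use is likelier after some products than others, a later rating mixes the assigned product with an effect of the previous one. Without data on the interval, this can be neither examined nor ruled out.

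**Working it through.** The plan states no figure on this point, so there is none to reproduce. The checks below use its design.

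**1. Orders that start with a pouch.** Three conditions give 3! = 6 orders. With C = cigarette, 3 = 3 mg and 6 = 6 mg, the Aim 1 orders are C36, C63, 3C6, 36C, 6C3 and 63C. Four of the six (67%) start with a pouch, and in all six at least one pouch comes before visit 3. In Aim 2 every condition is a pouch, so six of six orders start with one.

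**2. Visits that follow at least one study pouch.** Inputs are 40 participants (Aim 1) and 15 (Aim 2, from Statistical Considerations), all completing, with balanced orders.
- Aim 1: visit 2 gives 40 × 2/3 = 26.7 and visit 3 gives 40, so 66.7, or about 67 of 120 visits.
- Aim 2: 15 + 15 = 30 of 45 visits.

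These are opportunities for prompted home use, not observed use.

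**3. Time covered by the 12-hour rule.** The windows before visits 2 and 3 total 2 × 12 = 24 hours. Taking a week and a half as 10.5 days and 2 months as 60 days:
- 10.5 days: 24/252 = 9.5%
- 21 days (the ideal): 24/504 = 4.8%
- 60 days (the maximum): 24/1440 = 1.7%

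So roughly 90% to 98% of the time between the first and last visit has no documented restriction on pouch use and no question about it.

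**4. What counterbalancing does and does not remove.** Let cC, c3 and c6 be the shift in the next visit's rating caused by the previous product. Assume the six orders are used equally often and the shift reaches only the next visit.
- The 6 mg visit is first in two orders, follows 3 mg in two (C36, 36C) and follows the cigarette in two (C63, 3C6). Its mean shift is (2c3 + 2cC)/6 = (c3 + cC)/3.
- By the same count, the 3 mg visit has mean shift (c6 + cC)/3.
- Bias of the 6 mg minus 3 mg contrast = (c3 + cC)/3 − (c6 + cC)/3 = (c3 − c6)/3.

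The bias is zero if the two pouches prompt the same shift. Otherwise, each point of difference between c3 and c6 on the rating scale moves the contrast by a third of a point. If the shift lasted through all later visits, 3 mg precedes 6 mg in three of six orders and the reverse holds in the other three, so the bias would be (c3 − c6)/2. A period term does not change either result when the orders are balanced and complete, because each product then appears equally often in each period. The Aim 2 pairwise contrasts have the same form.

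**5. The two descriptions of the questionnaires.** Section 2 has a questionnaire before product use in its account of visits 1 to 3. Section 3, the only place that gives the content of the pre-intervention questionnaire, assigns it to Visit 1. Read together, pouch-use history is scheduled once.

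**The case against.** The strongest reply is that pouch use is both restricted and asked about: all nicotine is barred for 12 hours before each visit, this is checked in three ways, and repeated violations can end participation. A reader might infer from the gap that nothing at all is controlled, and the documents do not support that. These checks deal with acute nicotine carry-over. They do not speak to use days earlier: exhaled CO does not detect pouches, and plasma nicotine shows neither the product nor earlier use.

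Second, the questionnaire before each product, the attached surveys or the procedure manual may contain an interval question or an instruction. They are not in the supplied text, so this cannot be excluded. It does not override the explicit Visit 1 schedule, but it is a reason to reconcile the two sections first.

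Third, participants are blinded and learn their products only after visit 3. That weakens deliberate purchase of the same strength or brand, and so makes a difference between c3 and c6 less certain. It does not hide whether a visit involved a cigarette or a pouch, and it does not stop someone who liked a pouch from buying one.

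Fourth, no reason is given for the 3-month exclusion, and older pouch use is allowed, so the sample was never meant to be wholly pouch-naive. Subjective effects and intentions are also listed as exploratory objectives. Both points stand and limit the weight of the concern; the hypotheses still name appeal and intentions.

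Two size arguments are tempting and should not be used. The pilot survey's 25% current use and 33% trial among smokers give 25/33 = 76%, which a reader might take as uptake after a first pouch. It is a cross-sectional ratio in people who chose pouches themselves, and this trial screens out current users. Nor are all later Aim 1 visits exposed (80 of 120), because a third of second visits follow a cigarette.

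**Conclusion.** The gap is real and worth closing. Apart from the 12-hour pre-visit abstinence and its check, the supplied text neither restricts nor records pouch use between visits. About 67 of 120 Aim 1 visits and 30 of 45 Aim 2 visits follow a study pouch, assuming balanced orders and full attendance.

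The possible bias in the 6 mg minus 3 mg appeal and intention contrasts is (c3 − c6)/3 if the shift reaches only the next visit. Neither its size nor its direction can be given, because the documents contain no rate of home use among participants and no effect of such use on ratings. Two months is the maximum span, not the typical one; a bonus rewards completion within a month.

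A reader might infer that the nicotine delivery results, and with them the power calculation, are compromised too. The documents do not support that: each visit starts after 12 hours of abstinence with its own baseline plasma sample, so use days earlier should matter little. Nor does the adverse-event wording show that home use is expected. It is ambiguous and needs reconciling, no more.

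**What to change.** - **Measure.** At visits 2 and 3, before product use, add brief REDCap items covering the time since the last visit: days of pouch use with brand and strength, other nicotine use, cigarettes per day, and any quit attempt.
- **Instruct.** At visit 1, ask participants not to use pouches outside the clinic until the last visit, in line with the entry exclusion.
- **Analyse.** Keep all visits in the main analysis and add a period term for general drift across visits. Repeat the appeal and intention contrasts without visits preceded by home pouch use, labelled exploratory. That analysis conditions on behaviour after randomization and may selectively drop people who liked an earlier product, so it should not replace the main result.
- **Reconcile.** State whether the questionnaire before product use in section 2, Clinic Visits, is the one that section 3 schedules for Visit 1, and what is asked at visits 2 and 3. If a repeated form already covers interval use, saying so is enough for the measurement item. Reconcile the adverse-event wording in section 5 with single in-clinic use.

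The cost is about a minute at each of two existing visits, one sentence of instruction and one extra analysis. The questions may draw some attention to pouches. Interval data not collected at visits 2 and 3 would be hard to recover later.

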Data will be summarized descriptively. For hypothesis testing, we will use linear or logistic mixed effects regression models (with a random subject effect) to assess the main effects of product on plasma nicotine delivery, subjective effects, and behavioral intentions. Model assumptions will be checked, and variables will be transformed as needed. Missing data will not be imputed as likelihood-based linear mixed models will yield valid inference under missing at random assumptions. Models will control for age, sex, and other tobacco use if these features are not balanced by randomization. The same analysis strategy will be used for both aims. We calculated power for Aim 1 based on a repeated measures ANOVA comparing mean total nicotine delivery and maximum plasma nicotine concentration across 3 conditions; existing literature on differences in nicotine delivery across SLT products, including NPs, facilitates the use of this outcome for a power analysis.⁹ With a total sample size of only 20 participants and a Bonferroni-adjusted alpha of 0.017, we would have 84% power to detect a mean difference in total nicotine delivery of 25.7 ng/mL and 99% power to detect a mean difference of maximum nicotine concentration of 7.0 ng/mL between products.⁹ To account for attrition and the potential need for a larger sample size to detect differences in more subjective outcomes, we will recruit a

sample of 40 participants. For Aim 2, there are no known data to estimate effect sizes and thus to conduct power analyses. The sample size of 15 participants is intended to provide these data for future research.

5. Safety Management, Risks, and Benefits

Safety Management

Clinical Adverse Events

Clinical AE will be assessed by study staff at each study visit via participant self-report and managed immediately. Clinical AE may be related to nicotine overdose or the blood draw. Signs of nicotine overdose include nausea, vomiting, headache, presyncope, tachycardia, and disrupted sleep. With the blood draw, there is a slight risk of bruising, discomfort, and infection with blood draw. Study staff will be trained to recognize these signs and subjects will be encouraged throughout the visit to self-report any AE. In the event of a medical emergency, study staff will be advised to call 911 on the subject's behalf.

AE Reporting

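### Minute-0 plasma nicotine is collected at every visit but not applied to maximum nicotine concentration, and no plasma cut-off or data rule covers a visit where abstinence failed

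*Combined protocol and SAP*

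**What the plan says.** **Use of the minute-0 sample.** Section 3 (Study Procedures), under the baseline blood draw, gives it two uses. The first is abstinence: "3 mL venous blood sample will be collected for later analysis to confirm abstinence". The second is a baseline for one outcome: "This blood draw will also be used to establish baseline plasma nicotine levels to estimate total nicotine delivery". The sentence introducing the draw tells participants that "their abstinence will be confirmed at the time of visit via blood plasma nicotine analysis", which does not fit with a later assay.

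**Check before product use.** Section 3, under the exhaled CO test: "To check for abstinence from tobacco, participants will perform exhaled carbon monoxide testing", with a limit of 10 ppm. Participants also "confirm via self-report that they have not used any other nicotine products over the last 12 hours". The section does not expressly say that a failed CO test ends the visit.

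**Who may enter.** The exclusion in both aims is "Use tobacco products other than cigarettes >10 days per month", so less frequent use of e-cigarettes or smokeless tobacco is allowed. Nicotine pouch use in the past 3 months is excluded.

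**Analysis.** Section 4 (Statistical Considerations) powers Aim 1 on total nicotine delivery and on the maximum, with "99% power to detect a mean difference of maximum nicotine concentration of 7.0 ng/mL between products" at 20 participants and alpha 0.017; 40 are to be recruited. The mixed model has a random subject effect. Its named covariates are age, sex and other tobacco use, each only if unbalanced. Variables may be transformed. The same strategy serves Aim 2, planned there at 15 people to supply effect sizes.

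**Consequence of non-abstinence.** Section 4 (Subject Completion, Withdrawal, and Early Termination) allows discretionary removal, with repeated violations as an example. It has no rule for the data of a single visit.

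**The concern.** Nicotine present at minute 0 is still largely present when the product peaks, so an unadjusted maximum is product delivery plus whatever the participant brought to the visit. That carried-in amount can differ between one person's visits. A random subject effect removes only what is constant within a person, so the variation passes into every product contrast.

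The safeguard is weakest for non-smoked nicotine. Exhaled CO reflects smoke, and self-report is the only other check before the product is used. The plasma assay would reveal a failed visit, but only afterwards, and the plan does not say what value counts as failure or what then happens to the data.

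Most exposed are the 6 mg versus 3 mg contrast in hypothesis 1b, where the difference may well be smaller than 7.0 ng/mL, and Aim 2, whose means, ratios and variances are meant to feed later studies.

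**Working it through.** **1. The plan's figure.** Alpha: 0.05/3 = 0.0167, which rounds to the stated 0.017. The 99% cannot be verified because no SD is given. Back-solving a two-sided paired t test (n = 20, difference 7.0, alpha 0.017, power 99%) implies an SD of the paired difference of 6.12 ng/mL. With 38 error degrees of freedom it is 6.39; by the normal approximation, 6.64.

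**2. How much leftover nicotine remains.** Assume one compartment and half-life h. The fraction left at t hours is 0.5^(t/h). Sampling times: "Blood draws will be collected from the line at 0 5, 15, 30, 60, and 90-minutes".

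| h (assumed) | 5 min | 30 min | 60 min |
|---|---|---|---|
| 1 h | 0.94 | 0.71 | 0.50 |
| 2 h | 0.97 | 0.84 | 0.71 |
| 3 h | 0.98 | 0.89 | 0.79 |

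**3. How much a compliant participant brings.** At h = 2 h, 12 hours is 6 half-lives, leaving 1/64. A minute-0 value of 2 to 5 ng/mL would have needed 128 to 320 ng/mL 12 hours earlier. At h = 2.5 h the factor is 2^4.8 = 27.9, giving 56 to 139. Appreciable minute-0 values therefore come mainly from people who did not abstain.

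**4. Noise.** Let b be the visit-to-visit SD of leftover nicotine at the peak. The SD of a paired difference becomes √(6.12² + 2b²), taking 6.12 as free of this noise. For scale, if a fraction p of visits carries L ng/mL at the peak and the rest none, b = L√(p(1 − p)): p = 0.10 and L = 6.7 give b = 2.0; p = 0.20 and L = 10 give b = 4.0. All of b, p and L are assumptions, and so is the 3 ng/mL difference.

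| b | SD of difference | Power, 7.0, N = 20 | Power, 7.0, N = 40 | Power, 3, N = 40 |
|---|---|---|---|---|
| 0 | 6.12 | 99.0% | >99.9% | 72.5% |
| 2 | 6.74 | 97.1% | >99.9% | 62.7% |
| 4 | 8.33 | 86.0% | 99.7% | 42.3% |
| 5 | 9.35 | 76.0% | 98.5% | 33.3% |

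**5. Differences versus ratios.** Take assumed true pouch peaks of 7 and 3 ng/mL at 60 min and h = 2 h. With 2 ng/mL at minute 0 in both, the maxima are 7 + 0.71 × 2 = 8.42 and 3 + 0.71 × 2 = 4.42. The difference is still 4.0, but the ratio falls from 2.3 to 1.9. A simulation on the protocol's sampling schedule, with mean minute-0 levels from 2 to 8 ng/mL, gave differences of 3.95 down to 3.6 and ratios of 1.9 down to 1.4. At a mean of 8, the minute-0 sample was itself the maximum in 14% of visits with the weaker pouch. By step 3, such means are far above what compliance would leave; they bound the effect and do not predict it.

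**The case against.** The strongest reply is that little is at stake. Order is randomized and counterbalanced, so leftover nicotine should average out across products. Twelve hours of abstinence removes nearly all of it. Recent pouch users are excluded and other products are limited. Power for 7.0 ng/mL at 40 participants barely moves, and Aim 2 is not a powered comparison. All of that stands, and it limits the point to noise and ratios. It does not remove the point, because counterbalancing equalizes averages and does nothing for visit-to-visit variance or for a log-scale contrast.

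Several stronger readings are tempting, and the documents do not support them:

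- *That the minute-0 sample serves total delivery alone.* It is also collected to confirm abstinence.
- *That the maximum will be analysed as observed.* The plan does not define it either way. Section 3 refers blood processing and analysis to a procedure manual that is not among these documents. The outcome definition still belongs in the statistical text.
- *That non-smoked nicotine cannot be detected.* Self-report asks about it and the plasma assay would show it. What is missing is an objective check before product use.
- *That leftover nicotine could equal the whole powered difference.* At a 2-hour half-life, a visit starting at 7.0/0.841 = 8.3 ng/mL carries 7.0 at 30 min. But that is one visit against a mean difference: among 40 participants it moves a product mean by 7.0/40 = 0.18 ng/mL.
- *That the cigarette–pouch contrast is materially biased toward hypothesis 1a.* An early cigarette peak retains 0.97 − 0.84 = 0.13 to 0.97 − 0.71 = 0.26 of the minute-0 level more than a later pouch peak. Reaching 0.3 to 1.3 ng/mL needs a mean minute-0 level of 2 to 5 across all visits, which step 3 makes implausible under compliance.

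**Conclusion.** The point holds in a limited form. The plan collects a per-visit baseline, names it for total delivery and for abstinence, and does not carry it into the maximum-concentration outcome or the model. It also contradicts itself on when plasma confirms abstinence, and gives neither a cut-off nor a rule for a failed visit's data.

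The consequence is mainly lost precision from undeclared non-abstinence, with ratios pulled toward 1 if the maximum is log-transformed. The stated 7.0 ng/mL comparison at 40 participants is little affected. A smaller 6 mg versus 3 mg difference, and the estimates from Aim 2, are more exposed. The size rests on assumed leftover levels, half-life and peaks; the documents supply none of these. The change is worth making because it costs almost nothing, not because the main Aim 1 conclusion is in danger.

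**What to change.** 1. In Statistical Considerations, add that visit's minute-0 plasma nicotine as a covariate in the mixed models for maximum concentration, in both aims. This needs no half-life. Alternatively, define the maximum as baseline-corrected by subtracting C0·exp(−kt) from each later sample, with k = ln 2 / half-life. That addresses ratio shrinkage more directly on a log scale, at the cost of an assumed half-life.
2. Before samples are analysed, set a minute-0 plasma value above which a visit counts as failed abstinence for analysis purposes, and repeat the product comparisons without those visits as a sensitivity analysis.
3. Reconcile the Section 3 sentences on whether plasma confirms abstinence at the visit or by later assay.

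Cost: a few sentences, one degree of freedom per model and one extra analysis. The sample is already planned at every visit, so no further blood, visits or participants are needed.
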